3 BACKGROUND AND RATIONALE

Mechanical ventilation is the first line supportive treatment of acute respiratory failure in ICU subjects and ensures the replacement of gas exchange during respiratory failure in ICU subjects (2). Ventilation support should be adapted to cellular metabolism in order to provide necessary oxygen (oxygenation) and to eliminate carbon dioxide (ventilation).

In conventional ventilation modes, clinicians adjust and modify the oxygenation and ventilation parameters manually. Subjects in an ICU evolve continually, and parameters may not be optimal with manual adjustments (3). These manual adjustments represent a substantial workload for clinicians during subject care (4), as conventional ventilation modes compel them to adjust all parameters and modify adjustments when the physiological status of the subject changes.

Some ventilation modalities adjust ventilation automatically according to physiological parameters measured on the subject (5, 6). They have been proven beneficial with regards to ventilation optimization as adapted in real time to subject clinical condition, decreased care workload and ventilation duration (7, 8, and 9). Unnecessary high FiO_2 leading to hyperoxemia is detrimental. The ability to adjust FiO_2 to subject needs is likely beneficial for subjects and reduce costs. Currently, no automated oxygenation control is available on marketed ventilators for adult subjects in the US.

Adaptive Support Ventilation mode (ASV) has been used for 21 years in Europe and INTELLiVENT-ASV software accessory received CE marking in 2010 in Europe. It is a software accessory that fully automates Hamilton Medical's ASV mode, automatically adjusting both oxygenation and ventilation settings (10). The oxygenation parameters, FiO_2 and PEEP, are adjusted according to oxygen saturation measured by pulse oximetry (SpO_2). Ventilation is adjusted according to end-tidal partial pressure of carbon dioxide measurement (PetCO_2) in passive subjects (without spontaneous ventilation) and according to respiratory rate (RR) and PetCO_2 in active subjects (with spontaneous ventilation). The system can stabilize the subject in these optimal zones with maximum safety.

When target MV is determined, tidal volume (VT) and RR are determined according to the principle of the least respiratory work and force of breathing (11, 12). Clinicians choose target ranges for SpO_2 and PetCO_2 in addition to the limits for FiO_2 , PEEP, and inspiratory pressure.

INTELLiVENT-ASV safety and efficacy have been demonstrated in post-cardiac surgery (13) and in ICU subjects over periods of time up to 48 hours (10, 14). A randomized, cross-over, pilot study comparing INTELLiVENT-ASV mode to ASV in fifty (50) passive ICU subjects in Europe demonstrated better efficacy of ventilation, by delivering less volumes and pressures without alteration of gas exchange (10). The automatically selected parameters remained within the defined safety limits. The present study will assess safety and efficacy of INTELLiVENT-ASV in ICU subjects up to 7 days after enrollment.

3.1 Investigational device(s) and comparator(s)

Non automated ventilation arm:

Non automated ventilation mode (administered according to the ICU protocols), utilizing Hamilton Medical ventilator.

For those ventilators used for treating the subjects in the non-automated ventilation mode INTELLiVENT-ASV ventilation mode will not be selected.

It will be evaluated on a site by site cases if Hamilton Medical ventilators will be supplied by the Sponsor to be used for this study in the non-automated ventilation arm.

If there is a need to have the ventilators provided by the Sponsor upon completion of evaluation, Sponsor will supply the devices.

Automated ventilation arm:

INTELLiVENT-ASV ventilation mode, utilizing a Hamilton-Medical ventilator.

For those subjects in the automated arm the INTELLiVENT-ASV ventilation mode will be selected.

Sponsor will supply ventilation system, to be used for this study, if needed.

All subjects will be ventilated with a Hamilton ventilator equipped with SpO₂ and PetCO₂ sensors in order to assess the main endpoints.

INTELLiVENT-ASV is a software accessory that automatically adjusts ventilation and oxygenation parameters to keep the subject within clinician-set target ranges, from intubation until extubation.

It is a closed-loop ventilation mode and is intended as an accessory for currently marketed Hamilton Medical ventilators.

INTELLiVENT-ASV includes the following features:

1. Ventilation controller (% MinVol)
2. Oxygenation controller (FiO₂ & PEEP)
3. Quick Wean

The investigator brochure provides details on physiological inputs and sensor management.

Please refer to the Investigator Brochure for more details

3.2 Preclinical Evidence

Preclinical evidence is included in the Investigator Brochure.

3.3 Clinical Evidence to Date

Please refer to Annex B

3.4 Risks and Benefits Statement

Risks

Subjects suffering from critical illness and requiring invasive mechanical ventilation are exposed to numerous risks. First, critical illness in and of itself can cause numerous complications and mechanical ventilation may not always prevent a fatal outcome related to the underlying disease. Second, invasive mechanical ventilation is an invasive, potentially prolonged procedure that exposes the subject to specific risks of complications related to: Airway management (tracheal tube intubation), need of analgesia and sedation, infection, critical-illness neuromyopathy and thrombosis. Even in situations where mechanical ventilation can help improve gas exchange, inappropriate ventilator settings can lead to: ventilator-induced lung injury, lung barotrauma (pneumothorax) and iatrogenic alterations in O₂ and CO₂ arterial blood content. There is mounting evidence that not only low O₂ and high CO₂, but also low CO₂ and high O₂ can be deleterious to the critically ill subject. In short, the risks of invasive mechanical ventilation should be lower than the risks of the critical illness. Clinicians involved in the management of critically ill subjects continuously try to minimize these risks by periodical arterial blood gas sampling leading to regular iterative adjustments of the settings of the ventilator. In some instances, a continuous monitoring of PetCO₂ and SpO₂ is performed. Strategies aiming at limiting sedation and detecting as soon as possible the ability of the subject to be liberated from the ventilator are also systematically implemented, to minimize the time spent under invasive mechanical ventilation.

Both groups will be exposed to the risks inherent to invasive mechanical ventilation, such as ventilator malfunction and error in arterial blood gas measurements. Each ICU has specific strategies and policies to prevent and handle such problems.

Conceivably, risks specific to INTELLiVENT-ASV include erroneously setting respiratory condition or ideal body weight and sensor malfunction. To minimize the risk of erroneous setting, a specific training will be provided to all healthcare workers handling subjects included in the study (**refer to Annex C**). Regarding sensor malfunction, INTELLiVENT-ASV per design handles such occurrence by interrupting the close-loop automatic adaptations, keeping the ongoing setting and alarming the ICU team to the condition. They will then have the choice either to correct the sensor failure (a typical example would be a dislodged SpO₂ sensor due to subject's movement) or to enter new settings manually as in the control group. Furthermore, the attending physician has at any time the possibility to switch to conventional ventilation if she/he deems it necessary.

Although the above-mentioned situations are theoretically possible, preliminary studies have shown that among different groups of subjects, there is a safer ventilation with INTELLiVENT-ASV compared to conventional ventilation in volume (13).

Subjects are monitored as any ICU subject, with particular attention to ventilation parameters. The attending physician in the ICU always has the possibility to fall back to conventional ventilation for whatever reason.

The risk level is estimated to be moderate. The INTELLiVENT-ASV system was the subject of a risk analysis, and preliminary studies have not reported any adverse events related to INTELLiVENT-ASV during more than 200 hours of cumulative ventilation with INTELLiVENT-ASV (10, 13).

Benefits

The common health field benefit is to make available to this subject population, a ventilator that continuously adapts the delivered ventilation and oxygenation in real time to the needs of mechanically ventilated ICU subjects. These automations are a real progress in relation to the current procedures and above all may increase the safety of mechanically ventilated subjects.

The individual risk faced is therefore limited, and alarm settings can alert the physician in order to immediately correct as needed any ventilation or oxygenation anomaly. The potential overall benefit is high for ICU subjects. The benefit / risk balance does justify the study conduct as there is no additional risk anticipated for subjects – there may be the possibility to detect additional clinical benefits as outlined before.

4 STUDY OBJECTIVES

4.1 Overall objectives of the study

The study is designed to assess safety and efficacy of INTELLiVENT-ASV, a software accessory integrated in Hamilton ventilators that is designed to fully and automatically adjust both oxygenation and ventilation settings.

Efficacy and safety are primarily assessed to keep ventilation and oxygenation variables in optimal target ranges according to pertinent guidelines for Invasive Mechanical Ventilation.

4.2 Primary Objectives

Efficacy: To assess the efficacy of INTELLiVENT-ASV in adult ICU subjects up to 7 days after enrollment.

Safety: To assess the safety of INTELLiVENT-ASV in adult ICU subjects up to 7 days after enrollment.

4.3 Secondary Objectives

The secondary objective is the assessment of ventilation safety and effectiveness by measuring physiologic parameters, clinical outcomes associated interventions and typical clinical complications up to day 28 after enrollment.

4.4 Tertiary Objectives

Efficacy: To assess the efficacy of INTELLiVENT-ASV in adult ICU subjects from day 8 up to day 28 after enrollment.

Safety: To assess the safety of INTELLiVENT-ASV in adult ICU subjects from day 8 up to day 28 after enrollment.

5 STUDY ENDPOINTS

5.1 Primary endpoints

Primary endpoints will be measured continuously during ventilation period up to 7 days after enrollment.

Efficacy

Efficacy of the investigational device by assessing the ability to keep ventilation and oxygenation variables in optimal target ranges.

This endpoint will be determined by the percentage of time spent with six (6) variables in the optimal range:

- 1) Tidal volume (VT)
- 2) Maximum pressure (Pmax)
- 3) Oxygen saturation measured by pulse oximetry (SpO₂)
- 4) End-tidal partial pressure of carbon dioxide (PetCO₂)
- 5) Respiratory rate (RR) for spontaneous breathing subjects
- 6) Pmax-PEEP for passive ARDS subjects

The optimal and sub-optimal ranges are defined by pertinent guidelines for different clinical conditions including normal lungs, brain injury, ARDS, and chronic hypercapnia.

Safety:

The primary safety endpoint will be determined by percentage of time spent with at least one variable in the sub-optimal range during the first seven (7) days of enrollment.

For the invasive mechanical ventilation ranges, please refer to section 10.4.5 Analysis of Primary Endpoints.

5.2 Secondary endpoints

Secondary endpoints will be recorded continuously until the end of intervention period (up to 28 days after enrollment).

Efficacy

Physiologic parameters:

1. Respiratory mechanics (Compliance, resistance, expiratory time constant) will be assessed automatically breath-by-breath
2. Oxygenation (PaO₂/FiO₂, FiO₂, PEEP)
3. Ventilation (VT, RR, mechanical power will be assessed automatically breath-by-breath, ΔP , P_{PLAT}, will be assessed twice a day).

4. FiO_2 levels to be assessed in both study arms

Outcomes:

1. Duration of invasive mechanical ventilation: time between intubation and last extubation or death. When a subject is re-intubated within 48 hours after extubation, the period between extubation and re-intubation is considered as invasive ventilation days.
2. Duration of non-invasive mechanical ventilation: noninvasive ventilation refers to CPAP or pressure support NIV delivered before intubation or after extubation. High flow therapy is not considered in this calculation.
3. Total duration of mechanical ventilation: sum of duration of invasive and noninvasive mechanical ventilation.
4. Time from intubation to first successful SBT
5. Passive ventilation duration: passive ventilation is defined when the percentage of subject's triggered breath is lower than 25% of total respiratory rate.
6. Weaning duration: time between the first sedation cessation to the last extubation or the last disconnection from the ventilator for tracheostomized subjects. Subjects reintubated within 48h after extubation will be kept in the study. Subject re-intubated beyond 48h will be considered as weaned from the ventilation.
7. VFD to day 28 are defined as: the number of days from the time of initiating unassisted breathing to day 28 after start of ventilation, assuming survival for at least 48 hours and no re-intubation within 48 hours after initiating unassisted breathing and continued unassisted breathing to day 28.

NIV will be considered as assisted breathing. CPAP will not be considered as assisted breathing. Ventilator free days will be calculated separately for invasive ventilation support and any other ventilation support (invasive and noninvasive).

If a subject returns to assisted breathing (re-intubated within 48 hours) and subsequently achieves unassisted breathing to day 28, VFDs will be counted from the end of the last period of assisted breathing to day 28.

A period of assisted breathing lasting less than 24 hours and for the purpose of a surgical procedure will not count against the VFD calculation.

If a subject was receiving assisted invasive breathing on day 27 or dies prior to day 28, VFDs will be - 1.

For subjects transferred to another hospital or other health care facility, study data collection will be stopped but subject will be contacted via a phone call on day 28 post enrollment to assess VFD endpoint if possible:

- ICU and hospital length of stay (discharge).

- ICU mortality (if the subjects is hospitalized in another hospital than the investigational site)
- Non-intensive ventilation (NIV) duration
- 28 days mortality
- Ventilation duration for study period (if reintubated beyond 48h)

Dropout could occur when patients are ventilated for less than 24 hours after inclusion because of unexpected death, transfer to another ICU, or withdrawal of informed consent. A maximum dropout rate of 5% of these cases is expected.

Associated interventions:

1. Duration and doses of sedative infusion
2. Duration and doses of analgesic infusion
3. Duration and doses of vasopressors
4. Duration and doses of myorelaxant
5. Number of recruitment maneuvers
6. Time spent in prone position
7. Time spent with nitric oxide

Workload:

1. Number of manual adjustment will be collected in both ventilation arms until considered as weaned from the ventilation.

Safety:

The secondary safety endpoint will be determined by evaluating the number of Serious Adverse Events (all SAEs included) within 28 days of the enrollment and the rescue therapy requirement (APRV, high frequency ventilation, ECCO2R and ECMO).

In addition to better characterise the risk profile of the study population the following non-mechanical ventilation related adverse events will be recorded on study day 7 and 28.

- Severe Acute kidney injury (AKI) in need for CRRT/IHD
- Severe critical illness neuro-myopathy signs of tetraplegia affecting arms shoulder and neck with potential implication of respiratory muscle. Weakness is documented using the following score points: score 0 for no visible muscle contraction, score 1 for visible muscle contraction with no or trace movement, score 2 for limb movement, but not against gravity and score 3 for movement against gravity but not resistance.
- Severe critical illness encephalopathy leading to prolongation of mechanical ventilation. The most frequent causes being a metabolic or electrolyte disorder, systemic inflammation and other causes. Hypoxia, Stroke, intracranial bleeding, epilepsy and delirium. Encephalopathy is assessed using the GCS score and need to be reported is < 8 points.
- Withhold of weaning and/or withdrawal of mechanical ventilation because of treatment limitation related to patient wish or treatment futility due to irreparable single or multi-organ

failure affect mechanical ventilation strategy, weaning from mechanical ventilation up to withdrawal of mechanical ventilation.

- Extubation failure that is related to weaning process by itself or associated conditions based on the interpretation of the investigator.
- Need for tracheostomy that is related to a difficult weaning process or associated conditions based on the interpretation of the investigator.

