9.1 Recording and reporting of AEs

- **Recording:** Entry of an event into the clinical database by site staff as they “become aware” (Soladis System) or into the safety database by the safety team (VigOps). .
- **Reporting:** Sending a report to the National Competent Authority, EC/IRB. Sites are responsible for submitting reports to their IRB or EC in most countries.

The EASiVENT study includes a general ICU patient population in need of mechanical ventilation for at least 24 hours. This population includes critically ill patients spanning a variety of primary and secondary medical conditions that can cause AEs including severe disability and death irrespective of study participation. The expected mortality in EASiVENT Study patient population is around 30%.

Given the high acuity of diseases and morbidity related to ICU patient populations, not all AEs will be reported in the EASiVENT Study.

AE information will be collected throughout the study and reported to Hamilton Medical on the Adverse Event collected in the eCRF. The investigator is responsible for detecting, documenting and reporting AEs to Hamilton Medical through the eCRF or via a paper form if the eCRF is not available.

For AEs that require immediate reporting (see Table 4: Adverse Event Reporting Requirements), initial reporting may be done using the Events Form via email to VCLS VigOps (contact details will be provided in the investigational site file), or in the Serious Adverse Events form in the eCRF with as much information as is available. In case the investigator requires information from the Sponsor in an emergency situation, the contact details for emergency situations are given in the investigational site file.

Investigators in the US should submit Unanticipated Device Effects (UADEs) to their IRBs at the same time as notifying VCLS VigOps.

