3.2.2 Secondary endpoints

Secondary endpoints will be recorded continuously until the end of intervention period (up to 28 days after enrolment).

Efficacy

Physiologic parameters:

- Respiratory mechanics (Compliance, resistance, expiratory time constant) will be assessed automatically breath-by-breath.
- Oxygenation (PaO₂/FiO₂, FiO₂, PEEP)
- Ventilation (VT, RR, mechanical power will be assessed automatically breath-bybreath, ΔP , P_{PLAT} , will be assessed twice a day).
- FiO₂ levels to be assessed in both study arms

Outcomes:

• Duration of invasive mechanical ventilation: time between intubation and last extubation or death. When a subject is re-intubated within 48 hours after extubation, the period between extubation and re-intubation is considered as invasive ventilation days.

- Duration of non-invasive mechanical ventilation: noninvasive ventilation refers to CPAP or pressure support NIV delivered before intubation or after extubation. High flow therapy is not considered in this calculation.
- Total duration of mechanical ventilation: sum of duration of invasive and noninvasive mechanical ventilation.
- Time from intubation to first successful Spontaneous Breathing Trial (SBT)
- Passive ventilation duration: passive ventilation is defined when the percentage of subject's triggered breath is lower than 25% of total respiratory rate.
- Weaning duration: time between the first sedation cessation to the last extubation or the last disconnection from the ventilator for tracheostomized subjects. Subjects re-intubated within 48h after extubation will be kept in the study. Subject re-intubated beyond 48h will be considered as weaned from the ventilation.
- VFD to day28 are defined as: the number of days from the time of initiating unassisted breathing to day 28 after start of ventilation, assuming survival for at least 48 hours and no re-intubation within 48 hours after initiating unassisted breathing and continued unassisted breathing to day 28.

NIV will be considered as assisted breathing. CPAP will not be considered as assisted breathing. Ventilator free days will be calculated separately for invasive ventilation support and any other ventilation support (invasive and noninvasive).

If a subject returns to assisted breathing (re-intubated within 48 hours) and subsequently achieves unassisted breathing to day 28, VFDs will be counted from the end of the last period of assisted breathing to day 28.

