4.3.1 Intention-To-Treat (ITT) Population

The Intention-To-Treat population (ITT) will consist of all randomized subjects. Subjects who receive the wrong ventilation support will be analysed in the arm to which they were randomized. The ITT population will be used for primary, secondary, and tertiary efficacy analyses.

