4.4 Subgroup Definitions

Forest plots will be used to display results of primary endpoints and total duration of MV within the following subgroups listed below:

- Regions (US vs Europe)
- Study centers
- Gender

All efficacy tables and forest plots displaying primary and tertiary efficacy results will also be presented by treatment arm and for four groups based on subject condition at inclusion:

- Normal lungs
- ARDS
- Chronic Hypercapnia
- Brain injury

Additionally, forest plots to display primary and tertiary efficacy results by spontaneous and passive breathing subjects for the six ventilation and oxygenation variables will be reported:

1) Tidal volume (VT)

- 2) Maximum pressure (Pmax)
- 3) Oxygen saturation measured by pulse oximetry (SpO₂)
- 4) End-tidal partial pressure of carbon dioxide (PetCO₂)
- 5) Respiratory rate (RR) for spontaneous breathing subjects
- 6) Pmax-PEEP for passive ARDS subjects

Study centers will be pooled from largest to smallest until the pooled center had more than 5 subjects in each treatment group.

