7.2 Secondary Efficacy Variable

Secondary efficacy variables covering physiologic parameters, clinical outcomes, workload, safety events, typical clinical complications up to day 28 after enrolment and associated interventions will be assessed.

Please refer to section 3.2.2 of SAP for the complete list for the secondary efficacy endpoints.

Data will be expressed by median (interquartile range) or mean±SD and 95% confidence interval depending on the normality of the distribution assessed with Kolmogorov-Smirnov test. Between group differences will be performed using the 2 sample Z-test for normal variables or Mann-Whitney test for variables with a non-normal distribution. If applicable, a Bonferroni correction will be applied for pairwise comparisons corresponding to the sponsor's variable of interest.

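### Ventilation duration ends at death and is compared in all randomized subjects without a competing-risk analysis, so an arm with more early deaths can appear to ventilate for less time

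*Protocol*

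**What the plan says.** Protocol 5.2 (Outcomes, item 1), repeated in SAP 3.2.2, gives "Duration of invasive mechanical ventilation: time between intubation and last extubation or death". Item 3 inherits the rule: "Total duration of mechanical ventilation: sum of duration of invasive and noninvasive mechanical ventilation". Item 4 is "Time from intubation to first successful SBT", with nothing on subjects who die before passing one.

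For the population, SAP 4.3.1 states: "The ITT population will be used for primary, secondary, and tertiary efficacy analyses". For the test, SAP 7.2 states: "Between group differences will be performed using the 2 sample Z-test for normal variables or Mann-Whitney test for variables with a non-normal distribution". SAP section 4 sets significance at one-sided 0.025. Neither document plans a time-to-event, competing-risk or worst-rank analysis of duration.

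On mortality, Protocol 9.1 says: "The expected mortality in EASiVENT Study patient population is around 30" per cent. On prominence, SAP 4.4 says: "Forest plots will be used to display results of primary endpoints and total duration of MV within the following subgroups listed below"; the subgroups are region, study center and gender.

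Two other provisions bear on the point. VFD are set to -1 for death before Day 28 (Protocol 5.2, SAP 3.2.2), and SAP 8.6 tabulates deaths with their cause. SAP 4.8 allows multiple imputation under missing-at-random (MAR) for secondary analyses where needed.

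**The concern.** Liberation from the ventilator and death on it are opposite outcomes, yet the duration variable gives both the same value if they fall on the same day. A difference between arms then mixes speed of weaning with frequency and timing of death, and the planned tests cannot separate the two. If one arm has more early deaths, part or all of an apparent shortening may be mortality.

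The result will be visible. Total duration is the secondary endpoint named for the region, center and gender forest plots, and the Outcomes tables are produced at both interim analyses (SAP 10.1). The Protocol synopsis describes the study as the primary basis for a pre-market approval application. Duration and VFD could point in opposite directions, and no rule says how to read them together.

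The SBT endpoint has a different gap. Death does not end that clock; it leaves the subject without a value, and the SAP does not say whether that counts as missing data.

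**Working it through.** **The plan's figures.** The documents give no effect size, power or sample size for duration. The only sample-size figure is N = 254 for the co-primary endpoints. Simulating looks at 128/192/254 with the stated boundaries and a correlation of 0.85 in absolute value gives joint power 0.801, against the stated 0.80. N = 254 at 1:1 gives 127 per arm, used below.

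**Inputs from the documents.** Mortality about 30% (Protocol 9.1); 2-8 days of mechanical ventilation (Protocol Annex A, Table 10); follow-up 28 days; one-sided 0.025; VFD = -1 for death.

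**Assumptions not in the documents.** Constant daily extubation hazard h_e, equal in both arms (0.10, 0.14 or 0.20); constant death hazard h_d while ventilated; every death occurs on the ventilator.

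**Closed form, ignoring the Day-28 cut-off.** Mean duration = 1/(h_e + h_d) and death probability p = h_d/(h_e + h_d), so mean duration = (1 - p)/h_e. With h_e unchanged, moving p from 0.25 to 0.35 multiplies the mean by 0.65/0.75 = 0.867, a fall of about 13%. At h_e = 0.14 the means are 0.75/0.14 = 5.36 and 0.65/0.14 = 4.64 days.

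**Simulation with the Day-28 cut-off.** 127 per arm, 2,000 trials per scenario. The last three columns give the share of trials significantly favouring the test arm, which has the higher mortality wherever the arms differ.

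| h_e | Mortality, control vs test | Mean duration, control to test (days) | Duration, Mann-Whitney | Duration, Z-test | VFD, Mann-Whitney |
|---|---|---|---|---|---|
| 0.10 | 30% vs 30% | 6.82 to 6.81 | 1.6% | 2.4% | 2.1% |
| 0.14 | 30% vs 30% | 4.96 to 4.97 | 3.0% | 3.3% | 2.1% |
| 0.20 | 30% vs 30% | 3.50 to 3.51 | 2.2% | 2.4% | 2.4% |
| 0.10 | 25% vs 35% | 7.27 to 6.36 | 15.7% | 19.9% | 0.3% |
| 0.14 | 25% vs 35% | 5.30 to 4.63 | 16.7% | 20.7% | 0.4% |
| 0.20 | 25% vs 35% | 3.74 to 3.25 | 15.8% | 19.7% | 0.2% |
| 0.10 | 20% vs 40% | 7.74 to 5.90 | 49.6% | 60.1% | 0.0% |
| 0.14 | 20% vs 40% | 5.66 to 4.27 | 50.9% | 61.6% | 0.0% |
| 0.20 | 20% vs 40% | 4.01 to 3.00 | 49.1% | 60.8% | 0.0% |

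At 25% vs 35% the falls are 1 - 6.36/7.27 = 12.5%, 1 - 4.63/5.30 = 12.6% and 1 - 3.25/3.74 = 13.1%. With equal mortality the rates stay near 2.5%. VFD moves the right way: 16.74 to 14.82 days at h_e = 0.14 and 25% vs 35%.

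**Direction depends on timing.** Take survivors at 8 days in both arms, all deaths on day t, and a 10-point mortality excess. The apparent difference is 0.10 × (t - 8): -0.6 day at t = 2, -0.3 at t = 5, 0 at t = 8 and +0.4 at t = 12.

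**Survivors only.** Under constant hazards the exit time is independent of the exit cause, so survivors' mean is also 1/(h_e + h_d). In the simulation it falls from 5.34 to 4.66 days (h_e = 0.14, 25% vs 35%). Restricting to survivors reproduces the artefact.

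**Cumulative incidence.** In the same model, ignoring the cut-off, the proportion ever liberated is 1 - p: 75% against 65%. This moves in the correct direction.

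**The case against.** The strongest reply is that the plan already holds the remedy: VFD penalises death, deaths are tabulated by cause, and secondary outcomes are repeated in the MITT population, whose 24-hour recording minimum removes the very earliest deaths. These are secondary endpoints, and neither the co-primary conclusion nor N = 254 depends on them. All of that stands and limits the consequence. It does not remove the problem: duration is tested and plotted separately, nothing ties it to VFD or mortality, and MITT does nothing about deaths after 24 hours.

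A second reply is that the size is assumed. The 30% in Protocol 9.1 is mortality in the study population, not death on the ventilator. A death after final extubation does not shorten invasive duration, so fewer deaths on the ventilator would give a smaller effect. That also stands, as does the point that a Bonferroni correction, which SAP 7.2 allows if applicable, would lower the rates shown.

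A reader might infer more than the documents support:

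- That a more lethal arm will always look better. The sign depends on when deaths occur.
- That total duration is the only non-primary endpoint with subgroup forest plots. SAP 4.4 also gives them for tertiary efficacy, by subject condition and by passive or spontaneous breathing.
- That SBT times will be imputed for the dead. SAP 4.8 permits imputation where necessary; it does not say that an SBT that never took place is missing data.

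**Conclusion.** The point holds for invasive and total ventilation duration. A stated rule scores an early death like an early extubation, and the planned comparison has no protection against it. At a 10-point mortality difference (25% vs 35%), mean duration falls about 13% in the higher-mortality arm. The false-favour rate is 16-17% with Mann-Whitney and 20-21% with the Z-test, against 2.5%. These figures rest on constant hazards, equal extubation rates, 127 per arm and all deaths on the ventilator. They illustrate the mechanism and do not predict this trial's result. With equal mortality and timing there is no bias.

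The SBT point is separate and narrower: the rule for subjects who die first is absent, and the SAP leaves room for imputing a time to them.

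This should be corrected in the SAP, but it does not threaten the primary analysis.

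**What to change.** - **SAP 7.2:** compare arms on cumulative incidence to Day 28 of liberation from ventilation (using the 48-hour criterion already in Protocol 8.4) and of first successful SBT, with death as a competing event. Censor transferred subjects without further data at transfer. Alternatively, rank deaths worst, as VFD does.
- **SAP 4.8:** state that neither time is imputed for subjects who died.
- **Reporting:** keep raw duration, including its forest plots, as description only, shown beside VFD and mortality. Do not use a survivors-only comparison as the remedy.

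The cost is some SAP text, standard software and one more summary; no study procedure changes. The censoring rule is needed because study data collection stops at transfer, the Day-28 call is made only if possible, and the listed call items include no SBT date.
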